
11. MEASUREMENT OF HCQ EFFECT

11.1 PRIMARY OBJECTIVE

To assess the effect of HCQ on PAR-4, first compliance with HCQ planned dose regimen should be ascertained.

HCQ regimen compliance: pill diaries (Appendix D) and/or patient-reported HCQ compliance will be evaluated to assess participant adherence to HCQ daily regimen at follow-up clinic visits with study staff. Additionally, study staff may institute a telephone check with study participants on a PRN basis, should compliance to the HCQ regimen need to be monitored outside regular clinic visit schedule.

Participants who completed 80% of the planned HCQ doses will be considered evaluable for the Primary Endpoint, PAR-4 increase.

PAR-4 level will be assessed for each participant at the following timepoints:

- Enrollment/Baseline visit
- Day 14 post- HCQ initiation
- Day 30 of HCQ
- Day 60 of HCQ
- Day 90 of HCQ
- 6-month follow-up (during a standard of care visit)
- 12-month follow-up (during a standard of care visit)

It is expected that HCQ will induce an elevation of PAR-4 expression among 50% of the participants within the 90-day administration of HCQ. The elevation is expected to be a 50% increase from baseline PAR-4 levels among half of the study participants.

11.2 SECONDARY OBJECTIVES:

11.2.1 HCQ safety analysis and Treatment Toxicity: frequency and incidence tables of toxicity and AEs will be generated. Toxicity will be assessed using Common Terminology Criteria for Adverse Events V5.0 (for HCQ and for radiation therapy), as well as the Clavien-Dindo classification of surgical complications in the case of patients who underwent surgery (Appendix F). All patients will be evaluable for toxicity (HCQ) from the time of their first treatment with Hydroxychloroquine.

11.2.2 HCQ immunologic effect on PAR-4 Levels: as measured by serum (or plasma) blood collected at multiple timepoints. PAR-4 secretion is expected to come primarily from normal cells of the patient. The contribution of the tumor cells to serum levels of PAR-4 is expected to be minimal, but this has not been directly tested. Association between PAR-4 levels and clinical stage will be assessed.

11.2.3 Quality of Life: This is assessed by two validated patient-reported outcomes measures, the EORTC QLQ-C30 and QLQ-PR25 questionnaires. All items assessing symptoms and functional domains employ a 4-point Likert scale, with responses ranging from "Not At All", "A Little", "Quite a Bit" and "Very Much." Study participants will be instructed to choose one response per item. The EORTC **QLQ-C30** is a 30-item questionnaire assessing multiple domains of global health-related quality of life in cancer populations. It includes one global QOL rating, 5 functioning scales (physical, cognitive, emotional, role and social) and 9 symptom-specific subscales (fatigue, N/V, pain,

dyspnea, insomnia, constipation, diarrhea, appetite loss). The EORTC **QLQ-PR25** is a prostate cancer module meant for use among patients with prostate cancer in varying in disease stage and treatment modality (i.e., surgery, chemotherapy, radiotherapy, etc.), which complements the QLQ-C30. The QLQ-PR25 module comprises 25 items assessing disease symptoms, treatment side effects, sexual functioning and sexual activity. The functional scales are sexual activity and sexual functioning; the 4 symptom scales are urinary symptoms, bowel symptoms, hormonal treatment-related symptoms, and incontinence aid. All participants will complete items 1-19 as well as items 20-21 (which query current sexual activity). Completion of Items 22-25 are conditional on being sexually active (and comprise the Sexual Functioning subscale), and thus will only be completed by a subgroup of study patients. For interpretation of scores on the two EORTC QOL questionnaires, all of the scales and single-item measures range in score from 0 – 100. A high scale score represents a higher response level – so that a higher score represents a higher (“better”) level of functioning OR a higher (“worse”) level of symptoms. See **Appendix G** for additional details and the patient self-report questionnaires.

11.3 Four Types of Disease Progression

1. **PSA or Biochemical Progression:** defined as a PSA increase of $\geq 25\%$ and ≥ 2 ng/mL if PSA was ≥ 2 ng/mL from baseline (OR a PSA increase of $\geq 25\%$ if PSA was < 2 ng/mL at study enrollment).
2. **Symptomatic Progression:** defined as increasing pain from baseline-detected metastatic lesion. Time to first symptomatic event will be calculated from study enrollment until the event of symptoms due to metastatic disease.
3. **Local Progression of baseline-detected lesions depend on site:**
 - 3a. ***soft-tissue metastatic lesion:*** local progression is defined as an increase of $\geq 20\%$ in the largest tumor dimension with a minimum absolute increase of 5 mm. All lesions are considered target lesions, irrespective of size, if they are suspicious on choline PET-CT. See Appendix H.1 for RECIST v1.1.
 - 3b. ***bone metastases:*** local progression is assessed using the MD Anderson Cancer Center-criteria²⁶⁻²⁷, and defined as a $\geq 25\%$ increase in size of a measurable lesion or a $\geq 25\%$ increase in the size of ill-defined lesions on CT considered to be progression. MDA bone-specific response criteria in Appendix H.2.
4. **Distant Progression:** appearance of new metastatic lesions

11.4 Definition of Disease Assessments to evaluate Progression-Free Survival and ADT-Free Survival

11.4.1 ADT-Free Survival

Indications to start Androgen Deprivation Therapy include appearance of new metastases (i.e., progression to more than the three baseline-detected metastases, “distant progression”), or local progression of baseline-detected metastases.

ADT initiation can be considered at Symptomatic Progression or at PSA Progression. Additionally, CT C/A/P and/or fluciclovine or PSMA PET scans may be performed at the time of either Symptomatic or PSA Progression at discretion of the treating physician.

Date of ADT initiation will be recorded for each participant, accompanied by the reason for initiation.

ADT-free Survival is defined as the time between study enrollment until the start of ADT or death as a result of any cause. Patients who do not start ADT at the time of last follow-up will be censored at that time point.

- Initiation of ADT will be recorded if it occurs after initiation of HCQ. This will also be recorded for enrolled patients who have ADT initiation occurring after completion of surgery/radiation but prior to HCQ initiation (as this is exclusion criterion, the patient will be removed from the study).
- After HCQ administration is completed, survival status will be assessed at ongoing clinic visits for one year post-enrollment, and afterwards, annually for up to 2 additional years (i.e., at Year 2 post-enrollment and at Year 3 post-enrollment).

11.4.2 Progression-Free Survival (time to clinical progression)

Four types of progression are defined in 11.3. Progression is calculated from time of study enrollment until progression (per the 4 specified definitions) or death. Events for PFS are:

1. PSA or biochemical progression: defined as a PSA increase of $\geq 25\%$ and ≥ 2 ng/mL (if PSA was ≥ 2 ng/mL from baseline)
2. Symptomatic progression: increasing pain from metastatic lesion
3. Local progression of baseline-detected lesions: each metastasis is a target lesion independently assessed as:
 - soft-tissue lesions assessed per RECIST v1.1 (Appendix H.1)
 - bone lesions assessed per MDA bone-specific response criteria (Appendix H.2)
4. Distant progression: appearance of new metastatic lesions.

If an event is identified, then the time to the event will be recorded as the first instance where any of the above four situations occur.

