4.2 Enrollment Guidelines

Patients who have received previous treatment for prostate cancer with the intent to cure who have biochemical recurrence will undergo metastatic evaluation with imaging at baseline including fluciclovine or prostate-specific membrane antigen (PSMA) PET scan (preferred), bone scan, PET/CT and/or CT of the chest, abdomen, and pelvis as needed to assess for metastatic disease.

Biochemical recurrence for patients who have previously undergone radical prostatectomy is defined as a PSA ≥ 0.2 ng/dl. Patients who have biochemical recurrence following radical prostatectomy should have received postoperative radiotherapy to the prostate bed if no evidence of metastatic disease.

For patients who have previously undergone primary treatment of their prostate cancer with radiotherapy, biochemical recurrence is defined as an increase of 2 or more ng/dl above the nadir. Patients who have undergone primary radiotherapy will have pelvic MRI to rule out local disease as part of the requisite baseline imaging. Suspicious lesions within prostate bed will be assessed by biopsy.

Patients with 1-3 metastatic lesions on metastatic evaluation will be further screened per inclusion and exclusion criteria as noted above, Section 3. Initial localization of metastases will be recorded (node vs bone vs visceral).

Eligible patients will be identified by the principal investigator and co-investigators of this study. Potentially eligible patients will be screened in the University of Kentucky Markey Cancer Center clinics by the investigators, study personnel, and the Principal Investigator (PI). Upon obtaining proper consent, patients will be enrolled into the study.

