5.5 Duration of Therapy

In the absence of treatment delays due to adverse event(s), hydroxychloroquine treatment will continue for 3 months or until one of the following criteria applies:

- Disease Progression, assessed by standard of care and defined as either:
 - PSA progression (an increase in PSA > 25% above baseline at study entry), or
 - Symptomatic progression (increasing pain from metastatic lesion), or
 - Progression of baseline-detected lesions (soft-tissue lesions as assessed by RECIST and bone lesions as assessed by the MDA criteria (respectively, Appendix H.1 and Appendix H.2)).
Additionally, CT C/A/P and/or fluciclovine or PSMA PET scans may be performed at the time of either Symptomatic or PSA Progression at discretion of the treating physician.
 - Appearance of new metastatic lesions
- Intercurrent illness that prevents further administration of treatment
- Unacceptable adverse event(s)
- Patient decides to withdraw from the study
- General or specific changes in the patient's condition that render the patient unacceptable for further treatment in the judgment of the investigator

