
NOTES: * per standard of care ** at the discretion of the treating physician.
 
Legend: S = standard of care; R = research; PSA, prostate-specific antigen; PET, positron emission tomography scan; HCQ, hydroxychloroquine; PAR-4, prostate apoptosis response-4; PSMA, prostate-specific membrane antigen PET scan
 
1: Blood (1 tube) will be drawn at each of the 7 noted timepoints for PSA and PAR-4 levels; plasma is preferred (serum is acceptable). Timepoints may be +/- 72-hour window at Pre-study and Enrollment. For Day 14, Timepoints may be +/- 120-hour window. Timepoints may be +/- 28-day window at the 3-, 6- and 12-month f/u, coinciding with a clinic visit.
 
2: for collection of PBMCs (peripheral blood mononuclear cells): one tube per collection timepoint, slated for Day 0, Day 30 and Day 60. Day 0 and Day 30 timepoints have a +/- 14-day window. Day 60 has a +6 week window. This is explicated in greater detail in study lab manual.
 
3: QOL is assessed via EORTC QLQ-C30 + QLQ-PR25 at 4 timepoints 
 - at a clinic visit prior to initiation of HCQ - at a clinic visit; either the end of HCQ administration OR when HCQ is discontinued (if stop it early) - at 6-mos and 12-mos post-treatment. These final two QOL timepoints can be +/- 8 weeks, and conducted during a regularly scheduled, standard of care clinic visit. 
 
4: Requisite pre-study eye exam; Eye exam may be repeated during HCQ administration if vision complaints.
 
5: One tube of blood will be drawn at each of the 6 noted timepoints for serum PSA; this is standard of care for baseline and every 3 months (4 of the 6 draws), with two additional draws scheduled. Timepoints may be +/- 72-hour window at screening and enrollment.
 
6: Imaging at baseline, pre-study: Patients who have confirmed recurrent disease of the prostate are deemed ineligible for this trial. As such, all eligible patients will undergo standard of care imaging to identify metastases (initial evaluation of status/extent of recurrent disease), including: 6a: All eligible patients will undergo standard of care imaging to assess extent of metastatic disease at baseline; fluciclovine or PSMA PET scans are preferred; other scans (PET/CT scan, bone scan and/or CT of the chest, abdomen and pelvis) may be performed as needed at baseline to assess extent of metastatic disease, per standard of care. 6b: Additionally, eligible patients who have undergone radiation prior to study enrollment will have an MRI of pelvis (in addition to previously named imaging studies) to assess for recurrent local disease. Suspicious lesions of the prostate seen on MRI will be biopsied. 6c: Imaging on Study as work-up for disease progression: Once a patient is enrolled on-study, imaging to assess disease progression will proceed per standard of care, based on clinical indicators such as rising PSA and/or other clinical symptoms. Per RECIST 1.1, tumor re-evaluation scheduled every 6-8 weeks at the discretion of the treating physician based on clinical indicators. Notably, a rising PSA and/or other clinical symptoms could trigger a scan/imaging in an earlier timeframe.
 
7: Concomitant Medications will be assessed per standard of care at the discretion of the treating physician; during HCQ administration, Con Meds will be assessed with a particular focus on medications contraindicated for use with HCQ.
 
8: Height will be evaluated once while on-study. Height can either be assessed via the patient's medical record, and/or assessed directly (in conjunction with vital signs during a clinic visit)
 
9: ADT initiation: record date and reason for ADT initiation. Reasons for ADT initiation include: PSA/biochemical progression, Symptomatic Progression, Local Progression of baseline-detected lesions (either soft-tissue or bone lesions), or Appearance of new metastatic lesions.
											

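### PFS scoring accepts one unconfirmed 25% PSA rise, with no absolute minimum, in men entering below 2 ng/mL, and 11.3 and 11.4.2 disagree on whether those men have a PSA event at all

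*Combined protocol and SAP*

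**What the plan says.** **Definition.** Section 11.3, item 1, has two branches. Men at 2 ng/mL or above need a rise of at least 25% and at least 2 ng/mL. For the others a rise of 25% is enough "if PSA was < 2 ng/mL at study enrollment"; no absolute minimum is attached.

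**Use in PFS.** Section 11.4.2 states: "Progression is calculated from time of study enrollment until progression (per the 4 specified definitions) or death". That brings in both branches of 11.3. The numbered event list that follows, however, gives the PSA item only for men at 2 ng/mL or above. On timing, "the time to the event will be recorded as the first instance where any of the above four situations occur". Neither section asks for a repeat PSA, a minimum interval, or a period after local treatment in which rises are not counted.

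**A third wording.** Section 5.5, on stopping HCQ, uses "PSA progression (an increase in PSA > 25% above baseline at study entry", with no absolute minimum at any PSA level.

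**Who can enter below 2 ng/mL.** In 4.2, recurrence after "radical prostatectomy is defined as a PSA ≥ 0.2 ng/dl". After radiotherapy, entry needs a rise of 2 or more above nadir, so the low branch concerns mainly post-prostatectomy men. Their share of the 20 is not stated.

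**Draws.** Study Calendar footnote 5: "One tube of blood will be drawn at each of the 6 noted timepoints for serum PSA". The PSA row shows screening, Day 0, Day 30, Day 90, and 6 and 12 months after HCQ cessation. Footnote 1 differs: "Blood (1 tube) will be drawn at each of the 7 noted timepoints for PSA and PAR-4 levels". Under 5.3, HCQ starts two weeks before surgery or radiation.

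**The concern.** Below 2 ng/mL the threshold can be very small, and one value that crosses it fixes the PFS date for good. Two mechanisms can cross it without treatment having failed. One is ordinary assay and biological variation around an unchanged PSA. The other is continued growth at the pre-treatment rate, because the reference value is taken before local treatment and the first comparison comes soon after that treatment begins. A man whose PSA is up at Day 30 and down at Day 90 remains an event.

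PFS is the first-listed secondary endpoint. Section 13.3.2 reports it as a Kaplan-Meier median and as rates at specific times, and relates it to PAR-4 and PSA in exploratory Cox models. With a single arm, nothing offsets a bias toward early events. The disagreement between 11.3 and 11.4.2 adds a separate problem: two analysts could score the same low-PSA man differently, and both could cite the plan.

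**Working it through.** The plan gives no expected PFS, PSA variability or doubling time, so it has no figure of its own to reproduce.

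**Inputs from the documents**
- Threshold: ratio to baseline of at least 1.25 (11.3).
- Post-baseline draws: Day 30, Day 90, 6 and 12 months, so four comparisons (PSA row). If footnote 1 is taken literally, Days 14 and 60 are added and the rates below would be higher.
- Local treatment starts at about Day 14 (5.3), so Day 30 falls 30 − 14 = 16 days later.
- Screening labs may be up to 56 days before HCQ (5.1).

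**Assumed inputs.** Within-man CV of 5% to 15%; doubling time of 3 to 12 months.

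**Step 1: size of the threshold.**
- Entry PSA 0.2 (printed as ng/dl; read here as ng/mL, the unit in 11.3): 0.25 × 0.2 = 0.05.
- Entry PSA 1.9: 0.25 × 1.9 = 0.475.
- Entry PSA 2.0: the 2 ng/mL minimum governs, so PSA must double.

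**Step 2: variation only.** Lognormal error with σ = √ln(1 + CV²) on the baseline and on each draw. For one comparison with flat true PSA, P = 1 − Φ(ln 1.25 / (σ√2)). At CV 10%, σ = 0.0998 and P = 1 − Φ(0.2231/0.1411) = 1 − Φ(1.58) = 5.7%. The four comparisons share one baseline, so the chance of any hit was simulated (400,000 men):

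| True PSA course | CV 5% | CV 8% | CV 10% | CV 15% |
|---|---|---|---|---|
| Flat at all four draws | 0.3% | 7.5% | 16% | 35% |
| Flat at Day 30, 30% lower from Day 90 | about 0% | 2% | 6% | 15% |
| 20% lower from Day 30 | about 0% | <0.1% | 0.3% | 5.5% |

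Per 10 men below 2 ng/mL with flat PSA at CV 10%, that is 10 × 0.16 = 1.6 expected false events.

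For comparison, the upper branch at a true PSA of 3 gives 0% at CV 10% and 0.6% at CV 15%. That protection fades as PSA rises, because above 2/0.25 = 8 ng/mL the minimum no longer binds.

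**Step 3: growth only.** A rise of 25% by time t needs a doubling time of at most t × ln 2 / ln 1.25.
- From Day 0 to Day 30: 30 × 3.106 = 93 days, or 3.1 months.
- From a screening value at the full eight-week limit: (56 + 30) × 3.106 = 267 days, or 8.8 months.

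**Step 4: growth plus variation at Day 30.** With a Day 0 baseline, CV 10% and PSA not yet lowered by treatment, P = 1 − Φ((ln 1.25 − 30 ln 2/DT) / (σ√2)). For DT of 3, 4, 6 and 12 months this gives 51%, 36%, 22% and 12%.

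**Step 5: effect of confirmation, flat PSA.** If two consecutive draws must qualify, the rates at CV 5/8/10/15% become <0.1%, 1%, 3% and 11%. If a qualifying fourth draw is also counted because it cannot be confirmed, the same simulation gives 0.1%, 2.8%, 7.1% and 18.6%. How a last-draw rise is scored therefore decides much of the gain.

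**The case against.** The strongest reply is that the harm is conditional throughout. The 11.4.2 event list, read alone, gives men below 2 ng/mL no PSA event; they enter PFS only through the reference to 11.3. That is correct, and it is why the point cannot be put as though the plan were unambiguous.

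A reader might infer from the flat-PSA row that 16% to 35% of low-PSA men will be falsely scored. The documents do not support that. They give no CV, and at 5% the rate is negligible. A PSA that stays flat through 12 months is also an unfavourable assumption for men whose metastases are resected or irradiated at about Day 14; the table shows how quickly the rate drops once PSA falls.

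A reader might also take the 8.8-month doubling time as typical. It needs a screening PSA at the full eight-week limit as baseline, whereas 11.3 refers to enrollment and the calendar labels the Day 0 column as Enrollment/Baseline. From Day 0 the figure is 3.1 months, and the documents do not say how many men double that fast. Nor do they describe how soon PSA responds to surgery or radiation, so it cannot be said that treatment could not have acted by Day 30.

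Finally, PFS is secondary and descriptive, its Cox models are exploratory, and no decision rule uses it. That limits the weight of the point but does not remove it: no passage requires confirmation, and the two sections do disagree.

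**Conclusion.** The point holds in conditional form. By 11.3, and by reference in 11.4.2, one unconfirmed rise of 25% with no absolute minimum is a permanent PFS event for men below 2 ng/mL, while the 11.4.2 list omits that branch. The sections must be reconciled whatever the size of the effect.

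The size depends on a CV, a doubling time and a post-treatment PSA course that the documents do not give. It ranges from negligible (CV 5%, or PSA already falling by Day 30 at a modest CV) to material (16% of such men at CV 10% with flat PSA; 22% at Day 30 alone with a six-month doubling time, CV 10% and no treatment effect yet). The low branch concerns only men below 2 ng/mL, whose share is unknown, so no shift in median PFS can be stated. A reader might conclude that the trial's main result is compromised; it is not, because the primary PAR-4 test does not use PFS. This is a change that should be made, not a fatal flaw.

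**What to change.** For PFS scoring only, with no change to care:

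1. Make the PSA item identical in 11.3 and 11.4.2, stating whether men below 2 ng/mL have a PSA event, and name the Day 0 PSA as the baseline. Say also whether the different wording in 5.5 is intended; that stopping rule is otherwise outside this point.
2. Count PSA progression only if the next available PSA also meets the threshold, dated at the first qualifying value. If ADT or another PSA-lowering treatment starts, or another type of progression or death occurs, before the next PSA, the first value stands.
3. State in advance how a qualifying rise at the last available PSA is scored: for example, an event in the main analysis, and censored at the previous PSA in a sensitivity analysis.
4. Report PFS under the unconfirmed definition as a sensitivity analysis.

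The cost is endpoint wording and one extra analysis, using PSA values already scheduled or taken in routine care. The downsides are that confirmation after Day 90 may wait about six months for a scheduled draw, and that a rise at the final draw cannot be confirmed.

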12. DATA REPORTING AND REGULATORY REQUIREMENTS

Adverse event lists, guidelines, and instructions for AE reporting can be found in Section 7.

12.1 Method of Data Reporting

This study will require data submission and reporting via the OnCore Database, which is the official database of the MCC CRO. Instructions for submitting data are listed in the Data Management Plan created by the Markey Data Management staff in conjunction with the MCC CRO and the QA Office, per their SOPs (see S13.4, below).

12.2 Responsibility for Data Submission and Oversight

Study staff is responsible for submitting study data and/or data forms to OnCore as per the MCC CRO SOP's. This trial will be monitored by the MCC DSMC on a schedule determined by the PRMC at the initial PRMC review. The CRO SRF staff is responsible for compiling and submitting data for all participants and for providing the data to the PI for review.

